19. Has a history of primary immunodeficiency or an allogeneic organ transplant
20. Known history of previous clinical diagnosis of tuberculosis
21. Uncontrolled intercurrent illness including, but not limited to symptomatic congestive heart failure, uncontrolled hypertension, unstable angina pectoris, cardiac arrhythmia, active peptic ulcer disease or gastritis, seizures

Statistical Plan

There are multiple ongoing studies in various tumor types exploring the activity of nivolumab and ipilimumab. In a published report of the combination in patients with advanced NSCLC treated on a phase I study (Checkmate 012), treatment related serious adverse events were observed in 28% of patients (Hellmann Lancet Oncol, 2017). This study plans to accrue 20 patients, a sample size that would allow us to estimate grade 3 or higher acute drug related toxicity rate of 30% with a confidence interval of 20% (95% confidence level) or an upper bound of 50%. This would allow us to reasonably exclude a clinically significant increase in toxicity with the addition of radiation therapy to the nivolumab and ipilimumab combination as defined by the upper bound of the confidence interval.

Toxicities will be summarized as the number and percentage of patients with each type of toxicity. Responses will be summarized as frequencies and percentages. The Kaplan Meier method will be used to estimate overall survival and progression free survival. Outcomes will be calculated from the date of study entry to the date of the corresponding event. We will use multivariate statistics to test the hypotheses that pretreatment intratumoral immune cell phenotype and PD-L1 expression predict response to therapy, and that therapy alters systemic immunophenotype.

Study Schema

Note: refer to Dosing and Administration (Section 5.1.1) for further details on treatment scenarios.

Number of Centers: 1

Number of Subjects: A maximum of 20 subjects will be enrolled.

TABLE OF CONTENTS

STUDY SYNOPSIS	1
TABLE OF CONTENTS	11
ABBREVIATIONS AND DEFINITION OF TERMS.....	13
1. INTRODUCTION	19
2. STUDY OBJECTIVES	20
3. ETHICAL CONSIDERATIONS.....	21
4. INVESTIGATIONAL PLAN/STUDY DESIGN.....	22
4.2 Study Schema.....	22
4.3 Efficacy Measurements.....	24
4.4 Inclusion Criteria:	25
4.5 Exclusion Criteria:	27
5. TREATMENT	30
5.1 Systemic Therapy.....	30
5.1.1 Dosage and Administration	30
5.1.2 Definition of DLT.....	31
5.1.3 Dose Delays/Modifications.....	33
5.2 Radiation Therapy.....	36

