4.3 Efficacy Measurements

Adverse events will be monitored throughout the trial and graded in severity according to the guidelines outlined in the NCI Common Terminology Criteria for Adverse Events (CTCAE) version 5.0

Patients will be evaluated every 8 weeks (\pm 7 days) with radiographic imaging to assess response to treatment. CT or MRI will be used, per PI discretion, to scan areas of known disease. All imaging will be assessed using Response Evaluation Criteria in Solid Tumors (RECIST) 1.1 for determination of overall response rate (ORR) and progression-free survival (PFS).

4.4 Inclusion Criteria:

1. Histologically proven salivary gland carcinoma (WHO, 2005) arising from a previous head and neck primary site, and located within the head and neck region, lung or bone, and who are not candidates for curative intent therapy.
2. ≥ 18 years old at the time of signing informed consent.
3. Demonstrated disease progression during, or after discontinuation, of the most recent line of systemic therapy.
4. Have received any number lines of prior systemic therapy (including systemic therapy in the curative intent setting).
5. Have a target lesion/s deemed suitable by the treating physicians for SBRT with the intent of palliation or prevention of symptoms. This lesion must be:
 - a) 1-3 non-overlapping sites in the head and neck region OR
 - b) metastatic lesions outside the H&N region in the lung or bone (a minimum of 1 and a maximum 5 lesions will be irradiated), provided there is no significant overlap between the lesions.

Patients should have RECIST 1.1 criteria measurable disease in addition to the lesion/s treated with SBRT. If the site/s of SBRT were previously radiated to high dose RT (>50 Gy), there should be >6 month time interval between the last dose of radiation and the start of SBRT.

6. Have the ability to tolerate required SBRT-related procedures (e.g.: lie flat and hold position for treatment) as determined by the treating physician
7. Be willing and able to provide written informed consent for the trial and comply with the study visit requirements
8. Have measurable disease based on RECIST 1.1. (in addition to the lesion/s that will be treated with stereotactic radiation therapy)

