 - Grade 3 or 4 neutropenia that is not associated with fever or systemic infection that improves by at least 1 grade within 3 days. Grade 3 or Grade 4 febrile neutropenia will be a DLT regardless of duration or reversibility
 - Grade 3 or 4 lymphopenia
 - Grade 3 thrombocytopenia that is not associated with clinically significant bleeding that requires medical intervention, and improves by at least 1 grade within 3 days
 - Isolated Grade 3 electrolyte abnormalities that are not associated with clinical signs or symptoms and are reversed with appropriate maximal medical intervention within 3 days
- Grade 4 hematologic toxicity, not described in exclusions above
- Prolonged delay (>2 weeks) in initiating second dose of nivolumab or ipilimumab due to treatment-related toxicity
- Grade 5 toxicity, i.e., death

Dose modification/delays according to Section 5.1.3 will apply to the patients who experience DLTs in the run-in phase.

Immune-related AEs are defined as AEs of an immune nature (i.e., inflammatory) in the absence of a clear alternative etiology. In the absence of a clinically significant abnormality, repeat laboratory testing will be conducted to confirm significant laboratory findings prior to designation as a DLT.

During this DLT period, patients who received <90% of the nivolumab OR ipilimumab infusion on day 1 (e.g., because the infusion of either drug had to be discontinued due to an infusion reaction) and did not experience a DLT will not be taken into account in the assessment of the overall DLT rate for the phase I run-in cohort and will be replaced.

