5.1.3.3 Criteria for permanent discontinuation of nivolumab and ipilimumab

An individual subject will not receive any further investigational product if any of the following occur in the subject in question:

- The subject or legal representative (such as a parent or legal guardian) withdraws consent.
- Confirmation of PD and investigator determination that the subject is no longer benefiting from treatment with nivolumab and ipilimumab
- Dosing delays lasting 12 weeks or more
- Inability to reduce corticosteroid to a dose of ≤ 10 mg of prednisone per day (or equivalent) **within 12 weeks** after last dose of study drug/study regimen
- Recurrence of a previously experienced Grade 3 treatment-related AE following resumption of dosing
- Adverse event that, in the opinion of the investigator or the sponsor, contraindicates further dosing
- Subject noncompliance that, in the opinion of the investigator or sponsor, warrants withdrawal; e.g., refusal to adhere to scheduled visits
- Subject is determined to have met one or more of the exclusion criteria for study participation at study entry and continuing investigational therapy might constitute a safety risk

- Intercurrent illness that prevents further administration of treatment
- Investigator's decision to withdraw the subject
- The subject has a confirmed positive serum pregnancy test
- Noncompliance with trial treatment or procedure requirements
- The subject is lost to follow-up
- Completed all doses of study drug
- Grade ≥ 3 infusion reaction

Subjects may withdraw consent at any time for any reason or be dropped from the trial at the discretion of the investigator should any untoward effect occur. In addition, a subject may be withdrawn by the investigator or the Sponsor if enrollment into the trial is inappropriate, the trial plan is violated, or for administrative and/or other safety reasons.

Subjects who are permanently discontinued from receiving investigational product will be followed for safety, including the collection of any protocol-specified blood specimens, unless consent is withdrawn or the subject is lost to follow-up or enrolled in another clinical study. All subjects will be followed for survival. Subjects who decline to return to the site for evaluations will be offered follow-up by phone every 3 months as an alternative.

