^c To be done on each visit prior to administration of investigational drug. Concomitant medication collected up to the Safety Follow (-30 days post last dose of study treatment) or initiation of new anti-cancer treatment. AEs will be collected up to 100 days post last dose of study treatment or initiation of new anti-cancer treatment.

^d On weeks 1-24, see Section 5.1.1 for Nivolumab administration (-2/+3days), **nivolumab doses are given at least 12 days apart**

^e On weeks 25-52, see Section 5.1.1 for Nivolumab administration(-2/+3days) at a flat dose of 480mg, **nivolumab doses are given at least 12 days apart**

^f On weeks 1-24, see Section 5.1.1 for Ipilimumab administration(-2/+3 days) for 3 doses

^g XRT to begin 2 weeks after the first dose of Nivolumab and Ipilimumab and to be completed in 2 weeks

^h Add free T4 if TSH is abnormal. Repeat at least every 12 weeks.

ⁱ If screening laboratory assessments are performed within 3 days prior to Day 1 they do not need to be repeated at Day 1. Results for safety blood test must be available and reviewed before commencing an infusion. **During weeks 7-24:** CBC and serum chemistries will be done every 2 weeks prior to the nivolumab or nivolumab/ipilimumab infusions. **During weeks 25-52:** CBC and serum chemistries will be performed every 4 weeks prior to each nivolumab infusion.

^j Urinalysis performed at Screening and then as clinically indicated.

^k Coagulation tests: prothrombin time, aPTT and INR – only performed at Screening and then as clinically indicated.

^l Correlative blood samples will be collected on 3 occasions, prior to week 1, prior to week 8 and prior to week 16.

^m Timing of CT scans for tumor assessments will be every 8 weeks (+/- 7 days).

ⁿ If a subject initiates a new anti-cancer therapy within 30 days after the last dose of trial treatment, the 30 day Safety Follow-up visit must occur before the first dose of the new therapy. Once new anti-cancer therapy has been initiated the subject will move into survival follow-up.

^o Follow-up phase for patients that discontinue treatment for reasons other than disease progression (see Section 7.1.4.5).

^p Patients that have documented disease progression or starts treatment on new anti-cancer therapy will move into the survival follow-up phase.

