7.1.4.3 End of Treatment Visit

- Targeted physical examination
- Vital Signs and weight
- ECOG performance status
- Adverse event review/serious adverse event review
- Concomitant medication review

7.1.4.4 30-Day Post Last Treatment Visit

- Targeted physical examination
- Vital Signs and weight
- ECOG performance status
- Adverse event/serious adverse event review
- Concomitant medication review

7.1.4.5 Long-Term Follow-Up Visits every 8 weeks (\pm 7 days) for patients without documented progression/ have not started new anti-cancer therapy

- ECOG performance status
- Adverse event/serious adverse event review collection up to 100 days after last dose of study treatment
- Follow-up will continue until end of study

7.1.4.6 Survival Follow-Up -Every 12 weeks for patients with documented disease progression/have started new anti-cancer therapy

- Medical record confirmation or phone contact confirmation to document survival

- Adverse event/serious adverse event review collection up to 100 days after last dose of study treatment
- Follow-up will continue until end of study.

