8.4 STUDY STOPPING RULE

In keeping with the study primary endpoint, a stopping rule will be implemented in the unlikely event that the combination under study is deemed to have unacceptably high toxicities. Enrollment will be halted if more than 3 patients experience a Grade 4 or higher drug related toxicity (CTCAE v. 5) during the trial treatment period or up to 30 days after the last investigational drug infusion. The likelihood of observing more than 3 Grade 4+ drug-related adverse events is 80% if the true

rate is 20% and the likelihood is 91% if the true rate is 25%. This rule has an 83% chance of prematurely discontinuing trial enrollment after the 1st 10 patients are enrolled if the true rate of Grade 4 drug related toxicity is 40%. The study will be reviewed by the University of Washington/Fred Hutch Cancer Consortium Data and Safety Monitoring Committee (DSMC

STATISTICAL CONSIDERATIONS

All patients enrolled in the study, including those in the run-in phase will be included in the analysis of toxicity and efficacy.

Safety and tolerability is the primary endpoint of this study, and all patients enrolled will be assessed for this endpoint. Adverse events will be recorded and graded based on CTCAE v. 5, and their relationship to the experimental agents reported.

Similarly, all patients enrolled in the study (i.e., the initial 6 patient cohort, and the additional 14 patient expansion) will be included in the efficacy analyses. Clinical responses to the combination of nivolumab, ipilimumab and hypofractionated radiation will be based on RECIST 1.1 criteria. Oncologic outcome endpoints such as progression free and overall survival will be calculated from the date of study enrollment, until disease progression or death from any cause, respectively. Survival estimates will be calculated using the Kaplan-Meier method.

Exploratory endpoints of this study include correlative work performed on research serum and tissue samples.

Sample size determination

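### As worded, PFS ends at disease progression only, so a death without documented progression is not a PFS event and Kaplan-Meier PFS reads too high after it

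*Combined protocol and SAP*

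**What the plan says.** The only sentence that defines the time-to-event endpoints is in Statistical Considerations: "progression free and overall survival will be calculated from the date of study enrollment, until disease progression or death from any cause, respectively". The same section names Kaplan-Meier as the estimator and puts all enrolled patients in the efficacy analyses.

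The other places that mention PFS do not change this definition:

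- The synopsis and Section 2.2 only name PFS as a secondary objective.
- The synopsis Statistical Plan says "Outcomes will be calculated from the date of study entry to the date of the corresponding event" and does not say what that event is for PFS.
- Section 4.3 ties PFS to imaging read by RECIST 1.1 and does not mention death.

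No section gives a censoring rule for PFS.

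**The concern.** The sentence lists two endpoints and two end events, and *respectively* matches them in order: PFS with progression, OS with death. The other possible parse, in which PFS ends at progression or death, leaves no end event for OS. An analyst who follows the text therefore computes time to progression and reports it as PFS.

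The plan itself foresees deaths that this rule would miss:

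- Section 5.1.2 lists "Grade 5 toxicity, i.e., death" among the dose-limiting toxicities in a 12-week window, while the first scan is due at about week 8 (Section 7, footnote m). A toxic death before that scan would count in the primary safety endpoint but not as a PFS event.
- Section 5.1.3.3 states "Subjects who decline to return to the site for evaluations will be offered follow-up by phone every 3 months as an alternative". A death can then be known without any scan having shown progression.
- Patients who start new anticancer therapy before progression move to survival follow-up, and Section 7.1.4.6 lists no imaging there.

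What is at stake is the PFS curve and its landmark and median estimates. The primary safety endpoint, the stopping rule, OS and the sample size of 20 are not affected.

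**Working it through.** The plan gives no PFS target or event count, so there is no figure of its own to reproduce. The check compares the Kaplan-Meier estimate with these deaths counted as events against the estimate with them censored.

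**Inputs.** n = 20 (Section 4.1). Assumed: 10 first events by month 6 and no other censoring. The number d of those 10 that are deaths without progression is not in the documents; d = 1 and d = 2 are shown. The correct 6-month PFS is 10/20 = 50.0%.

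**Direction, death censored at its own date.** With r patients at risk, a death should multiply the curve by (1 − 1/r). Censored, it multiplies by 1. The risk sets are otherwise identical, so the curve is never lower than the correct one, and it is higher from the first such death until both reach zero. In 3,000 random data sets of 20 patients, with ties and other censoring, there was no exception.

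**Size at month 6, death by month 6:**

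| d | deaths before all progressions | deaths after all progressions |
|---|---|---|
| 1 | 10/19 = 52.6% | 11/20 = 55.0% |
| 2 | 10/18 = 55.6% | 12/20 = 60.0% |

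Other orderings fall between these limits. The limits are the same if the death is censored at an earlier scan. A death before the first scan, censored at enrollment, gives 10/19 = 52.6%.

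**Death after month 6, censored at a scan before month 6.** Here all 10 events by month 6 are progressions, and an 11th patient dies later. If k of the progressions fall between that patient's last scan and month 6, then S(6) = (10 + k)/20 × 9/(9 + k).

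- k = 1: 11/20 × 9/10 = 49.5%.
- k = 4: 14/20 × 9/13 = 48.5%.
- k = 10, the extreme: 20/20 × 9/19 = 47.4%.

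Before the death the correct value is 50.0%, so the estimate dips by 0.5, 1.5 or 2.6 points. Just after the death the correct value is 9/20 = 45.0%, so it is too high by 4.5, 3.5 or 2.4 points. The ratio of literal to correct after the death is (10 + k)/(9 + k), which always exceeds 1.

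**Effect on the median.** Assume exponential times and that a share q of first events are deaths without progression. A true median m then reads m/(1 − q). Section 1 gives historical medians of 5 to 6 months. At q = 10% these read 5/0.9 = 5.6 to 6/0.9 = 6.7 months; at q = 20%, 5/0.8 = 6.3 to 6/0.8 = 7.5 months.

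**Sampling error.** The 95% half-width at 50% with n = 20 is 1.96 × √(0.5 × 0.5/20) = 0.219, about 22 points.

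**The case against.** The strongest reply is that this is loose drafting. The endpoint is called progression-free *survival* throughout, nothing shows an intention to leave deaths out, and most analysts would include them from habit. The plan also never says that such deaths are censored; that follows only from reading the sentence literally and then applying Kaplan-Meier. This is fair as an account of intent. It does not rescue the text, because the sentence is the only operative definition and it states a different endpoint.

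The second reply is that little depends on it. PFS is secondary and descriptive, no threshold is tested, the bias is zero if nobody dies without documented progression, and the illustrated shifts lie within sampling error. All of this stands and limits the weight of the point. Still, after such a death the error runs in one direction, and it flatters the regimen.

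Third, the phone follow-up evidence is only partly relevant: many patients followed by phone will already have progressed. Those who stop for toxicity, or who start new therapy before progression, remain.

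Fourth, it is unclear how long scans continue. The schedule table, whose columns are broken in the available text, appears to place tumor assessments in long-term follow-up, but Section 7.1.4.5 lists no imaging there. Censoring at the last assessment depends on this. A death long after scans stopped would also count as an event at the death date, while a comparable living patient is censored at the last scan. That does not affect whether death belongs in the PFS event.

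**Conclusion.** The definition is wrong as written: it gives time to progression under the name PFS. Any death without documented progression that is censored leaves the Kaplan-Meier curve too high from that death until both curves reach zero. In the 20-patient illustration, one such death by month 6 adds 2.6 to 5.0 points to a correct 50.0%, and two add 5.6 to 10.0 points. The only downward error is a temporary dip between the last scan and the death, when censoring is at the scan. The sizes rest on assumed event counts, on no other censoring and, for the medians, on an exponential model. The direction after the death does not depend on those assumptions. This should be corrected, but it does not threaten the trial's primary conclusion.

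**What to change.** Replace the sentence in Statistical Considerations with:

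> PFS is the time from enrollment to first RECIST 1.1 progression or death from any cause, whichever comes first. Patients alive without progression are censored at their last tumor assessment, or at enrollment if they have no post-baseline assessment. OS is the time from enrollment to death from any cause.

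In the synopsis Statistical Plan, refer to this definition in place of the unspecified event. How to treat new anticancer therapy before progression is a separate choice for the sponsor and is not needed for this correction.

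The cost is one sentence and one cross-reference. Counting the deaths needs no new data: Section 5.1.3.3 states "All subjects will be followed for survival", and Section 7.1.4.6 provides for "Medical record confirmation or phone contact confirmation to document survival" every 12 weeks. For the censoring date, Section 7 footnote m already sets "Timing of CT scans for tumor assessments will be every 8 weeks"; Section 7.1.4.5 should be made consistent with the schedule table on whether scans continue in long-term follow-up. The one downside for the sponsor is that PFS may look slightly less favourable.

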7.1.2 Clinical Procedures/Assessments

7.1.2.1 Adverse Event (AE) Monitoring

The investigator or qualified designee will assess each subject to evaluate for potential new or worsening AEs as specified in the Schedule of Assessments (Section 7) and more frequently if clinically indicated. Adverse experiences will be graded and recorded throughout the study and during the follow-up period according to NCI CTCAE Version 5.0 (see Sections: 5.1.2, 8.2, 8.3). Toxicities will be characterized in terms regarding seriousness, causality, toxicity grading, and action taken with regard to trial treatment. AE collection will start once the subject signs consent and up to 100 days after the last dose of study treatment.

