8.1 DEFINITIONS FOR SERIOUS ADVERSE EVENTS

A **Serious Adverse Event (SAE)** is any untoward medical occurrence that at any dose:

- results in death
- is life-threatening (defined as an event in which the participant was at risk of death at the time of the event; it does not refer to an event which hypothetically might have caused death if it were more severe)

- requires inpatient hospitalization or causes prolongation of existing hospitalization (see **NOTE** below)
- results in persistent or significant disability/incapacity
- is a congenital anomaly/birth defect
- is an important medical event (defined as a medical event(s) that may not be immediately life-threatening or result in death or hospitalization but, based upon appropriate medical and scientific judgment, may jeopardize the subject or may require intervention [e.g., medical, surgical] to prevent one of the other serious outcomes listed in the definition above.)
Examples of such events include, but are not limited to, intensive treatment in an emergency room or at home for allergic bronchospasm; blood dyscrasias or convulsions that do not result in hospitalization.)
- Suspected transmission of an infectious agent (e.g., pathogenic or nonpathogenic) via the study drug is an SAE.

Although pregnancy, overdose, potential drug-induced liver injury (DILI), and cancer are not always serious by regulatory definition, these events must be handled as SAEs.

Any component of a study endpoint that is considered related to study therapy should be reported as an SAE (e.g., death is an endpoint, if death occurred due to anaphylaxis, anaphylaxis must be reported). Hospitalizations and/or death related solely to progression of the underlying disease will not be considered an SAE.

NOTE: (PI determines if this information regarding hospitalizations are considered SAEs and should be included in the protocol. This is supplemental information that is included in BMS-sponsored trials)

The following hospitalizations are not considered SAEs in BMS clinical studies:

- a visit to the emergency room or other hospital department < 24 hours, that does not result in admission (unless considered an important medical or life-threatening event)
- elective surgery, planned prior to signing consent
- admissions as per protocol for a planned medical/surgical procedure
- routine health assessment requiring admission for baseline/trending of health status (e.g., routine colonoscopy)

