There are multiple ongoing studies in various tumor types exploring the activity of nivolumab and ipilimumab. In a published report of the combination in patients with advanced NSCLC treated on a phase I study (Checkmate, 012), treatment related serious adverse events were observed in 28% of patients (Hellmann Lancet Oncol 2017). This study plans to accrue 20 patients, a sample size that would allow us to estimate grade 3 or higher acute drug related toxicity rate of 30% with a confidence interval of 20% (95% confidence level) or an upper bound of 50%. This would allow us to reasonably exclude a clinically significant increase in toxicity with the addition of radiation therapy to the nivolumab and ipilimumab combination as defined by the upper bound of the confidence interval.

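### The plan claims to rule out added toxicity from radiation on a Grade 3+ rate, but its only rate without radiation is for serious adverse events

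*Combined protocol and SAP*

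**What the plan says.** Under Statistical Considerations, Sample size determination (and again in the Synopsis, Statistical Plan), the argument has three parts.

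- **Reference.** In a phase I study of the two drugs in advanced NSCLC, "treatment related serious adverse events were observed in 28% of patients".
- **Precision.** "This study plans to accrue 20 patients", a number said to be enough to "estimate grade 3 or higher acute drug related toxicity rate of 30" (per cent). The precision claimed for that estimate is given as "with a confidence interval of 20% (95% confidence level) or an upper bound of 50" (per cent).
- **Inference.** The interval's upper limit is said to let the investigators "reasonably exclude a clinically significant increase in toxicity with the addition of radiation therapy to the nivolumab and ipilimumab combination".

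Elsewhere the protocol keeps seriousness and grade apart. Section 7.1.2.1 states: "Toxicities will be characterized in terms regarding seriousness, causality, toxicity grading, and action taken with regard to trial treatment". Section 8.1 defines a serious event by its consequence, for example one that "requires inpatient hospitalization or causes prolongation of existing hospitalization". Statistical Considerations says of the trial's own safety data: "Adverse events will be recorded and graded based on CTCAE v. 5".

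**The concern.** The third part is a comparative claim in a single-arm trial. To say that radiation has not raised a rate, one needs the same rate for nivolumab plus ipilimumab without radiation. The only such figure in the documents is 28%, and it counts patients with serious events, not patients with Grade 3 or higher events.

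Under this protocol's definitions the two sets overlap but differ. A drug-related Grade 3 laboratory value that leads to no admission and meets no other seriousness criterion counts as Grade 3+ toxicity but not as an SAE. A drug-related Grade 2 event that leads to admission is an SAE but not Grade 3+. Section 8.1 also requires pregnancy, overdose, potential drug-induced liver injury and cancer to be handled as SAEs, whatever the grade.

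Safety is the primary endpoint, so what is at stake is the main sentence the trial could write about radiation. With an unmatched reference, a reader cannot tell whether an upper limit near 50% is reassuring.

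**Working it through.** **Step 1. Reproduce the plan's figure.** Inputs from Sample size determination: p = 0.30, n = 20, 95% confidence (taken as two-sided). No interval method is named, so the Wald form is tried:

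- half-width = 1.96 × √(0.30 × 0.70 / 20) = 1.96 × 0.1025 = 0.201
- interval = 0.30 ± 0.201, that is 9.9% to 50.1%
- n for a half-width of 0.20 = 1.96² × 0.30 × 0.70 / 0.20² = 20.2

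The stated ±20 points, 50% and 20 patients all reproduce. The exact (Clopper-Pearson) interval for 6/20 is 11.9% to 54.3%, but the choice of interval is a separate matter.

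**Step 2. Set the two rates side by side.**

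| | Reference rate | Rate the trial estimates |
|---|---|---|
| Value | 28% | 30% (planning value) |
| Event | treatment-related, serious | drug-related, Grade 3 or higher, acute |
| Basis | seriousness (by outcome in this protocol's Section 8.1) | CTCAE v5 grade |
| Patients | advanced NSCLC | advanced salivary gland carcinoma |
| Time window | not given | not given in the sample-size text |

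No Grade 3+ rate for the two drugs without radiation appears anywhere in the documents, and no sentence links the 28% to the 30%.

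**Step 3. What a comparison with 28% would contain.** Let G1 be the Grade 3+ rate with radiation, G0 the Grade 3+ rate without it, and S0 = 28% the SAE rate without it. Then

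G1 − S0 = (G1 − G0) + (G0 − S0).

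The first bracket is the quantity the plan wants to limit. The second is the gap between the two measures. G0 is not given, so the second bracket has neither a known size nor a known sign. No corrected comparison can be computed.

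**Step 4. What the 50% limit means for different G0.** The values of G0 below are assumptions chosen to show the dependence; the documents support none of them. An upper limit of 50% excludes only increases above 50 − G0 points, treating G0 as known. The last two columns give the binomial chance, with n = 20 and no radiation effect, of seeing few enough events. The cut-offs are 6 or fewer (Wald upper limit 50.1%, as the plan rounds it) and 5 or fewer (exact upper limit 49.1%).

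| Assumed G0 | Increase excluded by a 50% limit | P(X ≤ 6) | P(X ≤ 5) |
|---|---|---|---|
| 20% | above 30 points | 91% | 80% |
| 30% | above 20 points | 61% | 42% |
| 40% | above 10 points | 25% | 13% |
| 50% | above 0 points | 6% | 2% |

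The same 50% limit could be lax or very strict, depending on a rate the plan does not supply. These columns do not measure the gap between SAEs and Grade 3+ events. They show only why a matched G0 is needed before the limit can be interpreted.

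**The case against.** **No comparison with 28% is planned.** A reader might infer a formal contrast between the observed Grade 3+ rate and 28%. The documents contain no such test or difference; the only threshold is the 50% upper limit, on the Grade 3+ scale. This objection stands. What remains is that the plan's stated conclusion is itself comparative, and 28% is the only figure that could serve as its reference.

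**The 30% is not said to come from the 28%.** Adjacent sentences and similar values invite that inference, but the text does not state it. The point does not need it.

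**The probabilities do not size the defect.** Correct. A result in 20 patients depends on the true rate whichever benchmark is cited, and the text sets no pass mark such as 5 of 20. The exact-interval column also adds a change of method that the plan did not make. It would be wrong to read either column as the bias from mixing the measures.

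**The cited study's own definitions are not in the documents.** Its SAE definition, time window, schedule and Grade 3+ rate cannot be checked here. The examples of diverging events therefore rest on this protocol's definitions. This is why no size or direction is claimed.

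**Other safety decisions are untouched.** The run-in uses DLTs and the stopping rule in Section 8.4 uses Grade 4 or higher drug-related toxicity; neither relies on 28% or 30%. This stands, and it confines the point to how the primary endpoint is interpreted.

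**Conclusion.** The concern holds in a limited form. The plan says that an upper limit of 50% on a Grade 3+ drug-related rate will exclude a meaningful increase from radiation. Its only rate without radiation is 28% for treatment-related serious events, a measure the protocol itself separates from grade. The 50% limit has no matched reference, so the comparative conclusion is unsupported as written, and no other section repairs it.

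The size and direction of the mismatch cannot be determined. A reader might conclude that the trial will overstate, or understate, the harm of adding radiation; the documents support neither, because the Grade 3+ rate without radiation is absent. The 20 patients and the ±20 points are sound as a statement of precision under the Wald method. Even with a matched rate, a single-arm result set against an NSCLC study could not isolate the effect of radiation.

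**What to change.** 1. Add a table giving the proportion of patients with at least one treatment-related SAE, with an exact 95% interval, and set it descriptively beside the 28%. Align the time window and SAE definition with the cited report as far as possible. Collection here runs to 100 days after the last dose (Section 8), and Section 8.1 both adds event types handled as SAEs and leaves some hospitalization exclusions to the principal investigator.
2. Keep the Grade 3+ rate as the main estimate. Justify its planning value and the 50% limit with a Grade 3+ treatment-related rate for the two drugs without radiation, on a comparable schedule and time window, and state what window *acute* covers.
3. If no such rate is available, withdraw the sentence about excluding an increase and describe the result as an estimate only.
4. In either case, state that the comparison is across studies and cannot isolate the effect of radiation.

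The cost is a wording change and one table. All SAEs are already collected, and causality is recorded under Section 8.2, so no extra patients or procedures are needed. The matched planning rate may be less favourable than 30%.
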